8.2.1. Pregnancy and Infant Outcomes

Pregnancy outcomes include pregnancy loss (pregnancy termination, spontaneous abortion, and fetal death [stillbirth]) and live birth (premature birth and full-term birth). Within each of these categories, the fetus or infant will be evaluated as to the presence or absence of anomalies or other fetal effects.

Pregnancy Loss

- Pregnancy termination (any induced or voluntary fetal loss during pregnancy)
- Spontaneous abortion (< 20 weeks of gestation)
- Fetal death, including stillbirth (fetuses born dead at ≥ 20 weeks of gestation or fetuses born dead at ≥ 350 g if gestational age is unknown), which is further classified as follows:
 - Early fetal loss (fetal death occurring at ≥ 20 weeks but ≤ 28 weeks of gestation)
 - Late fetal loss (occurring at \geq 28 weeks of gestation)

Live Birth

• Premature birth (delivered < 37 weeks)

CONFIDENTIAL

• Full term birth (delivered \geq 37 weeks)

Infant deaths up to 52 weeks of age, as defined in Section 9.3, will be reported among live births.

Major Congenital Malformations

- Interchangeably referred to as congenital malformations, congenital anomalies, and birth defects.
- Abnormalities in structural development that are medically or cosmetically significant, are present at birth, and persist in postnatal life unless or until repaired, as evaluated by independent advisors.

In addition, SGA births, abnormal postnatal growth and development (i.e., social/emotional, language/communication, neurocognitive, movement/physical development milestones) up to 2 years of age, ectopic pregnancies, and molar pregnancies will be reported for each pregnancy outcome (see Section 9.3). Given that SMA is a genetic condition, it is possible that babies born to an individual with SMA will also have SMA. Therefore, the diagnosis of SMA in infants will also be collected.

Maternal death during pregnancy, labor, delivery, or up to 12 weeks after delivery will be reported. Infant deaths occurring up to 52 weeks of age will also be reported.

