9.3.1.3. Birth Weight (Including Small for Gestational Age)

All live births will be classified as small, appropriate, or large for gestational age using the CDC definition of birth weight below the 10th percentile, between the 10th and 90th percentile, and above the 90th percentile, respectively. An infant's birth weight percentile and size for gestational age categorization will be based on World Health Organization growth charts or country-specific growth charts, as appropriate. Low birth weight (< 2500 g) will also be examined as an adverse pregnancy outcome.

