9.3.1.12. Abnormal Postnatal Growth and Development

Domains of developmental milestones (i.e., social/emotional, language/communication, neurocognitive, movement/physical development milestones) by age up to 52 weeks will be defined by guidelines provided by the CDC [CDC 2020]. As recommended by the

CONFIDENTIAL

CDC, the World Health Organization Growth Charts (suitable for use in the US from birth to 24 months) will be applied for this study, where infant growth measurements will be used to estimate gender-specific weight-for-length, head circumference-for-age, length-for-age, and weight-for-age percentiles.

Postnatal growth deficiency or FTT will be defined as weight in the < 10th percentile for sex and chronological age using international growth reference standards from WHO for children aged 0 to 24 months. Postnatal growth deficiency will be evaluated at 1, 2, 6, 12, 18, and 24 months of age.

Infant developmental deficiency will be defined as failure to achieve developmental milestones for chronological age defined by CDC. Infant developmental deficiency will be evaluated at 1, 2, 6, 12, 18, and 24 months of age.

Developmental milestones will be collected as part of routine clinical practice with pediatrician-determined results of infant status (i.e., below, above, or at age-appropriate achievement) in each of the domains listed above. "Ages and Stages" or similar standardized assessments may be collected for this study if performed as part of routine clinical care. No additional information will be mandated for collection as part of this study.

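### Growth and developmental deficiency are defined at chronological age and pooled over all live births, so infants born preterm can be classed as abnormal because of prematurity

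*Protocol*

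**What the plan says.** Section 9.3.1.12 of the protocol fixes two classifications by time since birth. Growth deficiency, or failure to thrive, is "weight in the < 10th percentile for sex and chronological age using international growth reference standards", taken from WHO. Developmental deficiency is "failure to achieve developmental milestones for chronological age defined by CDC". The visits are the same for every infant: "Postnatal growth deficiency will be evaluated at 1, 2, 6, 12, 18, and 24 months of age", and the same six ages apply to development. Milestone data come from routine care as "pediatrician-determined results of infant status (i.e., below, above, or at age-appropriate achievement"), with no statement of which age the pediatrician should use.

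Section 9.7.3.1.4 calculates the prevalence as events over all live births, with a binomial 95% CI. Its optional strata include gestational age at enrollment but not at birth. Section 9.7.3.2 allows comparison with MACDP and EUROCAT rates. Preterm infants are in the cohort: Section 8.2.1 lists "Premature birth (delivered < 37 weeks") as a category of live birth. Section 9.3.2.4 collects gestational age at birth, sex and weight.

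For birth weight, Section 9.3.1.3 says that "size for gestational age categorization will be based on World Health Organization growth charts or country-specific growth charts, as appropriate". The only WHO charts the protocol describes are those of Section 9.3.1.12: "World Health Organization Growth Charts (suitable for use in the US from birth to 24 months) will be applied for this study".

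**The concern.** Under both rules an infant born early is judged against infants who have had the same time since birth but a longer gestation. Some preterm infants will fall below the weight cut, or miss a milestone, only because they are younger in developmental terms. Premature birth is an outcome in its own right, so part of its frequency would reappear in a second outcome and look like a separate effect on growth or development.

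Infant outcomes belong to a primary objective (Section 8.2), and abnormal postnatal growth and development is one of the four outcomes that Section 9.7.3 names for prevalence and 95% CI. The protocol recognises the same problem for malformations: Sections 9.3.1.4 and 9.7.3 take prematurity-related defects out of the primary malformation analysis. It has no parallel provision for growth and development, where age at birth enters the classification directly. The limitations in Section 9.9 do not mention it.

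**Working it through.** The protocol gives no preterm rate and no expected rate for these outcomes, so there is no figure of its own to reproduce. The check has three steps.

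**1. Age offset.** Assume that term means 40 weeks and that a month is 4.345 weeks. Corrected age in weeks = months × 4.345 − (40 − gestational age at birth).

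| Visit | Chronological | Born at 32 weeks | Born at 36 weeks |
|---|---|---|---|
| 1 month | 4.3 | 4.345 − 8 = −3.7 | 4.345 − 4 = 0.3 |
| 2 months | 8.7 | 8.69 − 8 = 0.7 | 8.69 − 4 = 4.7 |
| 6 months | 26.1 | 26.07 − 8 = 18.1 | 26.07 − 4 = 22.1 |
| 24 months | 104.3 | 104.28 − 8 = 96.3 | 104.28 − 4 = 100.3 |

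The offset is constant in weeks but shrinks relative to age. For birth at 32 weeks it is 8/26.07 = 31% of chronological age at 6 months and 8/104.28 = 8% at 24 months. The largest effect is therefore expected at the early visits.

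**2. Effect on the weight classification at one visit.** Assumptions, none of them from the documents:
- Weight z-scores are standard normal in term infants, and in preterm infants once age is corrected.
- At uncorrected age they lie lower by *d* = 0.5, 1 or 2 SD in preterm infants.
- The preterm share is *s* = 10%, 20% or 40%.

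The 10th percentile is z = −1.2816.

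P(flag | preterm) = Φ(−1.2816 + *d*)
- *d* = 0.5: Φ(−0.7816) = 21.7%
- *d* = 1: Φ(−0.2816) = 38.9%
- *d* = 2: Φ(0.7184) = 76.4%

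Overall flag rate = (1 − *s*) × 0.10 + *s* × P(flag | preterm)

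| Preterm share | d = 0.5 | d = 1 | d = 2 |
|---|---|---|---|
| 10% | 11.2% | 12.9% | 16.6% |
| 20% | 12.3% | 15.8% | 23.3% |
| 40% | 14.7% | 21.6% | 36.6% |

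With corrected age (*d* = 0) every cell is 10% by construction. The excess is thus 1.2 to 26.6 points over the whole grid, and 1.2 to 5.8 points for a share of 10% to 20% and a shift of 0.5 to 1 SD. Milestones are not modelled, because the documents give no distribution to work with.

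**3. Scale in this study.** Section 9.5 expects 20 pregnancies. Section 7.1.2 gives a background miscarriage risk of 15% to 20%. Ignoring other losses and multiple births, live births number 20 × 0.85 = 17 or 20 × 0.80 = 16. With 17, the expected number flagged is 17 × 0.112 = 1.9 up to 17 × 0.366 = 6.2, against 17 × 0.10 = 1.7. Exact 95% CIs are 1.5% to 36.4% for 2/17 and 6.8% to 49.9% for 4/17. A doubling of the point estimate would stay within the first interval.

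**The case against.** **The preterm/term split is already there.** Section 8.2.1 says that small-for-gestational-age (SGA) births and abnormal growth and development are reported for each pregnancy outcome, and those outcomes include premature and full-term birth. On that reading, a cluster of abnormalities in preterm infants would be visible. This stands, and it rules out saying that prematurity would go unseen. It leaves the pooled prevalence, its CI and any external comparison unchanged.

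**Pediatricians may correct informally.** Some may, when they rate achievement. But the stated definition says chronological age and nothing records which age was used. The weight rule involves no such judgement.

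**Details are left to the SAP, and the study is too small to mislead.** The protocol itself states the age basis, so an SAP that made corrected age primary would contradict it. The comparison is optional and depends on numbers, and the intervals will be wide. That lowers the severity but does not make the definition right.

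**Stronger readings that the documents do not support:**
- A reader might infer that SGA will be read from the postnatal weight-for-age charts, giving every newborn one reference whatever the gestation. Section 9.3.1.3 classifies size for gestational age, leaves the choice to appropriateness and does not name those charts. A gestation-specific reference is permitted; it is just not required.
- A reader might take every preterm infant as falsely flagged: with 16 live births and 2 to 6 preterm (assumed), 2/16 = 12.5 to 6/16 = 37.5 points. That needs every one to be flagged at chronological age and none after correction. The 32-week example is also well below the 37-week threshold; at 36 weeks the offset is 4 weeks, not 8.
- A reader might link the rule to the neurobehavioral findings in mice (Section 7.1.1). Neurobehavioral impairment is a separate variable in Section 9.3.1.13 with no chronological-age rule, and the weight percentile has no direct bearing on it.

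**Conclusion.** The point holds for growth and developmental deficiency. The definitions fix chronological age for all infants, the denominator pools all live births, and no section corrects for gestational age at birth, so infants born before 37 weeks can be classed as abnormal because of prematurity. The direction of the bias is upward. Its size cannot be derived from the documents: the range of about 11% to 37% against 10% rests wholly on the assumed preterm shares and SD shifts, covers weight only, and assumes that age correction removes the whole shift. For SGA the finding is only that the reference is not named tightly enough. Severity: should-fix.

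**What to change.** In Section 9.3.1.12:
- For infants born before 37 weeks, define the primary weight-percentile and milestone classifications at age corrected for gestational age at birth.
- Keep chronological age as a sensitivity analysis.
- Show preterm and term infants separately, with the pooled figure.
- Where a pediatrician's milestone rating is used, record whether corrected age was applied, if that information is available. This should not be a compulsory field, because the section rules out requiring data beyond routine care.

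In Section 9.3.1.3, state that the SGA reference must be specific to gestational age and sex, so that the postnatal weight-for-age charts of Section 9.3.1.12 are not used for SGA.

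The weight and SGA changes need no new data, since gestational age at birth, sex and weight are already collected. The cost is some extra derivation at the registries, which hold the individual data while the sponsor receives only aggregate tables (Section 9.4). The primary figures also become less directly comparable with any external rate based on chronological age; the sensitivity analysis covers that.

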9.3.1.13. Neurobehavioral Impairment

Neurobehavioral impairment will be assessed in infants at 2, 6, 12, 18, and 24 months based on evaluation by the pediatrician through examinations/assessments conducted in usual clinical practice.

9.3.1.14. Pregnancy Complications

The following pregnancy complications will also be monitored and reported during the study:

- Pre-eclampsia: Primary pre-eclampsia will be based on HCP-reported diagnosis. It is often defined as the presence of hypertension on 2 occasions at least 4 hours apart after 20 weeks of gestation (in an individual with a previously normal blood pressure) and proteinuria; or, in the absence of proteinuria, a new-onset hypertension accompanied by 1 of the following conditions: thrombocytopenia, renal insufficiency, impaired liver function, pulmonary edema, or cerebral or visual symptoms. Eclampsia is a severe, life-threatening complication of pre-eclampsia that results in seizures.
- Pregnancy-induced hypertension: High blood pressure (elevated: systolic between 120 and 129 and diastolic less than 80 mmHg; Stage 1 hypertension: systolic between 130 and 139 or diastolic between 80 and 89 mmHg; Stage 2 hypertension: systolic at least 140 or diastolic at least 90 mmHg) associated with pregnancy, as diagnosed by the treating HCP.
- Preterm labor: Preterm labor will be based on HCP-reported diagnosis. It is often characterized as regular contractions of the uterus resulting in changes in the cervix that start before 37 weeks of pregnancy. Any interventions or

Spinraza (Nusinersen) SMA Pregnancy Exposure Study Within Existing SMA Registries

treatments provided to the participant as a result of preterm labor will be collected.

- Gestational diabetes: Gestational diabetes will be based on HCP-reported diagnosis. It is often characterized by the development of carbohydrate intolerance with first onset or first recognition during pregnancy. A record of an oral glucose tolerance test during pregnancy will also be accepted for data collection, where available.
- Placenta previa: Placenta previa will be based on HCP diagnosis. It occurs when the placenta fully or partially covers the mother's cervix.

9.3.2. Information Collected at Each Timepoint

Refer to Table 5 for the recommended study contact schedule.

9.3.2.1. Enrollment

It is expected that information will be collected at the time consent is provided for the pregnancy study, as permitted by local regulations. The primary reporter of this information will be the participant and may be supplemented by information from the participant's HCP or electronic medical records. Data that have been collected as part of the core registry protocol will also be used, as applicable.

An example of the information that will be collected is as follows:

- Reporter
 - Medical specialty, if HCP
 - Telephone number and email address of the reporter
 - Date that pregnancy is reported to the registry
- Participant demographic and contact information
 - Birth year and race
 - Height
 - Weight
 - BMI will be calculated
 - Years of education
 - Occupation
 - Employment status
 - Complete name, address, telephone number, and email address*
 - Name, address, telephone number, and email address of a secondary contact outside of the participant's household in case the participant cannot be contacted*

Spinraza (Nusinersen) SMA Pregnancy Exposure Study Within Existing SMA Registries

*This information will be kept confidential and will remain on site. It will not be recorded in the data collection system or included in the study database.

- Medical history
 - Surgical and medical history
 - Relevant medical diagnoses/conditions, including but not limited to scoliosis, wheelchair use, and respiratory function
 - SMA history and genetic testing results
- Family medical history
 - Family history of adverse pregnancy outcomes, MCMs, and developmental delays
 - Family history of multiple births
- Pregnancy history
 - Previous pregnancies
 - o Complications (e.g., pre-eclampsia, adverse reactions to medication)
 - Pregnancy outcome (e.g., live birth, spontaneous abortion, pregnancy termination)
 - o MCMs or developmental delay
 - o Birth length and birth weight of all previous live-birth infants
- Current pregnancy information
 - Date of LMP
 - EDD
 - Method of pregnancy confirmation
 - Health assessments
 - Prenatal testing
 - Outcome (if reported retrospectively)
- Pregnancy outcome risk factors
 - Smoking
 - Caffeine use (> 200 mg per day)
 - Alcohol use
 - Recreational drug use
- Nusinersen exposure history

- The participant's complete prior and current nusinersen exposure will be captured, with dates for doses prior to and during pregnancy. If the exact dates are unavailable, the HCP or participant will provide the best approximation available (e.g., week).
- Other prior (up to 6 months before conception) and current medications (including folic acid and vitamins)

9.3.2.2. Each Trimester

It is expected that the registry will collect the following information from the participant (if consistent with local regulations) or HCP or electronic medical records at each trimester:

- Changes in participant contact information
- Changes in secondary contact information
- Pregnancy outcome risk factors
 - Smoking
 - Caffeine use (> 200 mg per day)
 - Alcohol use
 - Recreational drug use
- Changes in pregnancy status (if a pregnancy outcome has occurred, a pregnancy outcome assessment must be performed; see Section 9.3.2.4)
- Gestational age (in weeks)
- Weight gain during pregnancy
- Nusinersen exposure history and adherence
 - The participant's nusinersen exposure history will be captured, with dates for doses prior to and during pregnancy, if not already collected at an earlier timepoint. If the exact dates are unavailable, the HCP or participant will provide the best approximation available (e.g., week).
 - Delayed or missed doses (with reason) over the course of the pregnancy.
- Other current medications (including folic acid and vitamins)
- Complications during pregnancy (e.g., pre-eclampsia, adverse reaction to medication) with associated notable dates (e.g., onset, resolution)

9.3.2.3. Prenatal Follow-up

It is expected that the registry will collect changes in the following information from the participant's HCP at approximately 6 to 7 months of gestation for the Prenatal Follow-Up:

- Participant contact information
- Secondary contact information
- Medical history
- Pregnancy outcome risk factors
 - Smoking
 - Caffeine use (> 200 mg per day)
 - Alcohol use
 - Recreational drug use
- Prenatal testing
- Pregnancy status
- Gestational age (in weeks)
- Weight gain during pregnancy
- Nusinersen exposure history and adherence
 - The participant's nusinersen exposure history will be captured with dates for doses prior to and during pregnancy, if not already collected at an earlier timepoint. If the exact dates are unavailable, the HCP or participant will provide the best approximation available (e.g., week).
 - Delayed or missed doses (with reason) over the course of the pregnancy
- Other current medications (including folic acid and vitamins)
- Possible SMA symptoms as determined by the HCP (e.g., muscle weakness, change in gait, tremor, respiratory changes)
- Complications during pregnancy (e.g., pre-eclampsia, adverse reaction to medication) with associated notable dates (e.g., onset, resolution)

9.3.2.4. Pregnancy Outcome Follow-up

It is expected that the registry will collect the following information from the participant's HCP on record, from other practitioners, from electronic medical records, or from the participant, as needed, at approximately 4 weeks after the EDD:

- Pregnancy outcome risk factors
 - Smoking
 - Caffeine use (> 200 mg per day)
 - Alcohol use
 - Recreational drug use
- Weight gain during pregnancy

CONFIDENTIAL

- Nusinersen exposure history and adherence
 - The participant's nusinersen exposure history will be captured with dates for doses prior to and during pregnancy, if not already captured at an earlier timepoint. If the exact dates are unavailable, the HCP or participant will provide the best approximation available (e.g., ± week).
 - Delayed or missed doses (with reason) over the course of the pregnancy
- Other current medications (including folic acid and vitamins)
- Possible SMA symptoms as determined by the HCP (e.g., muscle weakness, change in gait, tremor, respiratory changes) from the Prenatal Follow-Up assessment until the pregnancy outcome
- Pregnancy outcome (e.g., live birth, stillbirth, fetal loss, pregnancy termination [including reason, e.g., related to SMA, nusinersen, other], fetal anomaly)
- Type of delivery (e.g., vaginal, cesarean delivery [C-section]), including whether labor/delivery was induced early and, if applicable, the reason for induction
- Complications during pregnancy (e.g., pre-eclampsia, adverse reaction to medication) or birth (e.g., birth asphyxia) with associated notable dates (e.g., onset, resolution)
- Neonatal illnesses (e.g., prematurity, respiratory dysfunction, birth trauma) that resulted in hospitalization, including any treatments (e.g., drug therapies)
- Infant characteristics
 - Gestational age at birth (in weeks)
 - Sex
 - Weight and length
 - Head circumference
 - Birth order (for multiple births)
 - Apgar scores
 - Breastfeeding status (whether the infant is breastfeeding, bottle-fed, or both, as well as duration of breastfeeding, if applicable)
 - Genetic diagnoses, including SMA
 - Medications
 - Any MCM noted, including description and attribution
- Any untoward medical occurrence related to a pregnancy outcome, including neonatal illnesses, that could constitute an SAE as defined in Section 11 will also be reported.

The registry will contact the participant's HCP earlier in the pregnancy for outcome data if the participant reports an adverse pregnancy outcome or a pregnancy termination. Additional information and reports will be requested and collected for adverse pregnancy outcomes in the mother and infant as necessary, including autopsy and other pathology reports.

9.3.2.5. Pediatric Follow-up

It is expected that the following information will be collected from the pediatric HCP (or the participant, as necessary) when the infant is approximately 1, 2, 6, 12, 18, and 24 months of age:

- Pediatric illnesses (e.g., prematurity, respiratory dysfunction, birth trauma) that resulted in hospitalization, including any treatments (e.g., drug therapies)
- Infant characteristics
 - Head circumference
 - Feeding behavior
 - Weight and length
 - Developmental milestones (including postnatal growth deficiency or failure to thrive [FTT], infant development deficiency, and neurobehavioral impairment). Note: neurobehavioral impairment will be measured starting at 2 months of age.
 - Breastfeeding status (whether the infant is breastfeeding, bottle-fed, or both, as well as duration of breastfeeding, if applicable)
 - Genetic diagnoses, including SMA
 - Medications
- Evidence of any abnormality since last follow-up

Additional information and reports will be requested and collected for adverse pregnancy outcomes in the mother (i.e., death up to 12 weeks after delivery) and infant as necessary, including autopsy and other pathology reports.

